Are there risks of social	harm to the participants associated with the research?
If yes, describe:	
ii yes, describe.	
Are there economic risks ☐ Yes ⊠ No	s associated with the research?
If yes, describe:	
	Minimal Risk and the study presents the prospect of direct benefit to the participants Minimal Risk and the study presents no prospect of direct benefit to the participants, but will likely yield
generalizable	knowledge about the study question.
Minimizing Risks	
How will you minimize r	risks or discomfort?
✓ Monitor the ex ✓ Provide oppor	xperiments by professional staff. rtunities for rest or breaks. of participant based on specific criteria, explain: All participants who are terminated from the study will
	have the reason for their termination documented. Reasons for termination may include: lost-to-follow- up, participant-initiated withdrawal, physician-directed withdrawal, completion of study. At the end of the study or if the patient withdraws early, the investigator will discuss follow-up with the participant to ensure the participants receive appropriate ongoing follow-up according to local standard of care.
	cipant of his/her opportunity to stop or withdraw.
Other, describ	of process, explain: be:

Last Revised 01/2016 Page 17 of 22

Potential Benefits

Benefits to participants do NOT include monetary incentives paid in return for participation.

Please describe any direct benefits anticipated for the individual participants in this study:

There may be no direct benefits to the individual participants in the study. However, they may have short or long-term improvements on their pain symptoms.

Please describe any potential benefits to society:

Developing of a new method for the treatment of pain in Gulf War Illness patients.

Last Revised 01/2016 Page 18 of 22

DATA PRIVACY & CONFIDENTIALITY
The principal investigator/faculty sponsor is responsible for taking all necessary steps to maintain confidentiality of data. This includes coding data and choosing appropriate and secure ways to store data to prevent unauthorized access to the data.
Will identifiers or links to an identifier of the participants be stored? ⊠ Yes □ No
If yes, what information that could be linked to the participants will be recorded? All data collected in this study will be coded. Identifying information, such as name, DOB, physical and contact email addresses and phone numbers, which link a particular participant to their coded data, will be kept in a locked file cabinet in [name] lab. This information will be stored alongside the signed consent forms. All coded data will be kept in a separate locked file in [name]'s lab
Please explain the procedure for de-identifying or anonymizing the data: In order to safeguard our participants from a breach in confidentiality, all research data is coded with a unique semi-random subject identifier (URSI). All data after initial entry into the study database is coded based on this participant's number. [name] will have oversight over the stored data. There will not be any personally identifiable information stored in the research database.
Will you obtain any information containing personally identifying information? ☑ Yes ☐ No
If yes, please continue with the following questions.
If information with personal identifiers will be accessed, will the participants provide consent for storing of personal data or biological specimens in connection with the research? Yes No
If no, provide justification for a waiver of informed consent:
Will anyone other than the specified study team, have access to the study records or data? If so, please specify each person's name, role on this study, and affiliation. Non-compliance/ unanticipated problems, adverse events, audits and investigation reports will be reported to Human Research Protection Office, USAMRMC Office of Research Protections
If coded or identified data will be released outside of UTD or its affiliated institutions, please specify the persons/agencies to which the information will be released. Please also indicate the precautions that will be taken to assure that confidentiality will be maintained during transmission of the data. De-identified data will be available to [name] in his role as a subcontract PI at UT Southwestern. [name] is Professor of Internal Medicine and Director of the Division of Epidemiology in the Internal Medicine Department at UT Southwestern Medical Center and holder of the U.S. Armed Forces Veterans Distinguished Chair for Medical Research Honoring America's Gulf War Veterans. He has conducted extensive research on Gulf War Illness and aid in recruiting, study design, analysis, interpretation of the findings, and manuscript
writing. Coded data might be shared with the Human Research Protection Office, USAMRMC Office of Research Protections, in case of non-compliance/unanticipated probems, adverse events, audits and investigation
Will your study involve obtaining individually identifiable health information from health care plans, health care clearinghouses, or health care providers? ☐ Yes ☑ No ☐ Not Applicable
If "Yes," describe the procedures you will use to comply with the HIPAA Privacy Rule:
Where, how long, and in what format (such as paper, digital or electronic media, video, audio, or photographic) will data be kept? In addition, describe what security provisions will be taken to protect this data (password protection, encryption, etc.). All hard-copy clinical and research data, as well as electronic data, collected during this study will be kept in locked file cabinets or on password-protected computers in the laboratory of [name]. Data will be stored indefinitely.
What will happen to the data after the data analysis is complete?
Data will be destroyed years after completion of the study

Last Revised 01/2016 Page 19 of 22

☐ Data will be stored an unspecified length of	time
--	------

Last Revised 01/2016 Page 20 of 22

IRB REVIEW CATEGORY

THIS SECTION MUST BE COMPLETED

The DHHS and other Federal Regulations require that the IRB is responsible for determining whether the proposed data collection meets the federal definition of research.

Federal regulations state all activities classified as research must be submitted for IRB review and approval.

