
Last Revised 01/2016 Page 4 of 22

Given the promising results for pain symptoms in fibromyalgia patients, we aim to explore this treatment option for Gulf War illness patients with pain symptoms

What information do you expect to obtain and how will the obtained knowledge be applied:

To investigate the effects of repeated sessions of tDCS targeting the occipital nerve field on pain symptoms and on global and specific symptoms in GWI participants, we will measure possible changes in symptoms (using questionnaires) and electrophysiological brain activity (resting-state EEG) in a group that receives active tDCS and a group that receives sham tDCS.

The primary outcome measure for pain symptoms will be measured by the Visual Analogue Scale (VAS).

VAS. The Visual Analogue Scale consists of a straight line of 10 cm with the endpoints defining extreme limits such as 'no pain at all' and 'pain as bad as it could be'. The patient is asked to mark his widespread muscle pain level on the line between the two endpoints. The distance between 'no pain at all' and the mark then defines the subject's pain. VAS will be assessed for pain severity. It has been used to measure symptom relief and treatment satisfaction. Several studies have demonstrated that the VAS is sensitive to treatment effects (Haefeli & Elfering, 2006). The VAS has been found to correlate positively with other self-reporting measures of pain intensity. In addition, the difference in pain intensity measured at two different points of time by VAS represents the real difference in magnitude of pain which seems to be the major advantage of this tool compared to others. This will be performed both during Phase I as well as during Phase II after 4-weeks, 12-weeks, and 24-weeks of treatment.

The secondary outcome measures will include measures of of global change as well as changes in specific symptoms of interest related to the Center for Disease Control (CDC) clusters, as GWI is a complex disease with multiple symptom manifestations: Cluster A by the Modified Fatigue Impact Scale (MFIS) and the Pittsburgh Sleep Quality Index (PSQI); Cluster B, mood and cognition, will be assessed by Beck Depression Inventory (BDI); and Cluster C by the Pain Catastrophizing Scale (PCS), McGill Pain Questionnaire (MGPQ), and Pain Vigilance and Awareness Questionnaire (PVAQ).

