Participant's Review of Inclusion/Exclusion Criteria: Prospective participants will initially review general inclusion and exclusion criteria about the study on the recruiting materials where there is contact information to contact a researcher for more detailed information about the study.

Interested individuals will be screened through a phone screen script. Their continued interest in the study confirms that they have met (via self-report) basic inclusion/exclusion criteria.

Administration of Consent Form: When the Consent form is administered, participants will have already acknowledged that they have met the above criteria and have expressed continued interest in participating in the study. If, at that time, they feel that they do not meet these criteria, or have specific questions about these criteria, they will be asked to inform the research team member administering the consent form. If they again meet these criteria to the best of their knowledge, a second set of study screening procedures will be administered to evaluate whether or not they qualify for the study. All of the remaining screening and study procedures described hereinafter will be administered only if the participant has provided consent to participate (i.e., signed the consent form).

It is an eleven day study with four follow-up sessions: 1 week, 4 weeks, 12 weeks and 24 weeks after the last day of stimulation.

Session 1: Pre-tDCS Assessment (approximately 3 hours)

Assessment: At [name]'s lab, The following questionnaires/tests will be administered:

- 1. VAS. The Visual Analogue Scale
- 2. MFIS. Modified Fatigue Impact Scale
- 3. PSQI. Pittsburgh Sleep Quality Index
- 4. BDI. Beck Depression Inventory
- 5. PCS. Pain Catastrophizing Scale
- 6. MGPQ. McGill Pain Questionnaire
- 7. PVAQ. Pain Vigilance and Awareness Questionnaire

In addition, changes in electrophysiological brain activity will be measured using resting-state EEG.

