Resting state EEG. The EEG procedure is a non-invasive technique that will record brain electrical activity while the participant sits quietly in a chair for 5 minutes with their eyes are closed. In order to do that, a cap with 64 electrodes will be placed on the scalp. The cap is similar to a loose nylon swim cap. The cap will be placed on the participant's head and then a small amount of a salt water mixture will be added to each electrode from the outside of the cap. The cap placement will take up to 30 minutes. This is a common clinical procedure carried out in neurology.

Session 2-10: tDCS stimulation (approximately 45 minutes)

tDCS Stimulation - Participants will be randomly assigned to two different groups after they have finished assessment: the first group will receive real tDCS targeting the occipital nerve field. This group will receive 20 minutes of stimulation targeting the occipital nerve field area consisting of a current of 1.5mA. The second group (sham, or control, group) receive the same procedure for tDCS but with no delivery of electrical current. For both groups, the stimulation current will gradually ramp up to 1mA during the first 60 seconds of stimulation but the current will only persist for real tDCS group.

Session 11: tDCS stimulation + Immediate Post-tDCS Assessment (approximately 3.5 hours)

tDCS Stimulation - Participants will receive tDCS for 20 minutes (1) at 1.5 mA targeting the occipital nerve field area, or

Last Revised 01/2016 Page 14 of 22

(2) with no delivery of electrical current (sham, or control, group). For both groups, the stimulation current will gradually ramp up to 1mA during the first 60 seconds of stimulation but the current will only persist for real tDCS group.

Immediate Post-tDCS Assessment - Participants will complete the following assessments that were part of the Pre-tDCS assessment:

- 1. VAS. The Visual Analogue Scale
- 2. MFIS. Modified Fatigue Impact Scale
- 3. PSQI. Pittsburgh Sleep Quality Index
- 4. BDI. Beck Depression Inventory
- 5. PCS. Pain Catastrophizing Scale
- 6. MGPQ. McGill Pain Questionnaire
- 7. PVAQ. Pain Vigilance and Awareness Questionnaire
- 8. Resting state EEG.

Sessions 12 (1 week after), 13 (4 weeks after), 14 (12 weeks after) and 15 (24 weeks after) - Post Assessments (approximately 2.5 hours):

Post-assessments will take place at 1 week after, 4 weeks after, 12 weeks after and 24 weeks after the last tDCS session. Follow up-tDCS Assessment are:

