### 4. Data Collection Timeline

- **Assessment Points:**
  - **Baseline:** Pre-treatment assessment.
  - **Immediate Post-Treatment:** After the 10 tDCS sessions.
  - **Follow-Up:** 4 weeks, 12 weeks, and 24 weeks post-treatment.

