### 6. Statistical Analysis Plan

#### A. Primary Outcome Analysis: Pain Severity (VAS)

- **Modeling:** Mixed-effects repeated-measures ANOVA with group (treatment vs. sham) as a between-subjects factor and time (baseline, immediate post-treatment, 4-week, 12-week, 24-week) as a within-subjects factor.
- **Post-Hoc Tests:** Bonferroni-adjusted post-hoc tests will examine specific time points if interaction effects are significant.
- **Intention-to-Treat (ITT) and Per-Protocol Analyses:**
  - **ITT:** Last observation carried forward (LOCF) for missing data.
  - **Per-Protocol:** Include only participants with at least 8 out of 10 therapy sessions completed and no interfering medications.

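### The primary VAS baseline is a single Session 1 mark; a second mark at Session 2, before stimulation, would make change from baseline more precise without another visit

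*Protocol*

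**What the plan says.** The Protocol Summary makes the VAS the primary outcome ("The Visual Analogue Scale consists of a straight line of 10 cm") and supports the choice with the statement that "the difference in pain intensity measured at two different points of time by VAS represents the real difference in magnitude of pain". It quotes test-retest figures for the PSQI (.85) and the BDI-II (.93) but none for the VAS.

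Under Methods and Procedures the VAS is listed once at Session 1, once at Session 11 and once at each follow-up session. Sessions 2-10 list stimulation and no VAS. The schedule is described thus: "It is an eleven day study with four follow-up sessions". Eleven days fits one assessment day plus ten stimulation days (Sessions 2 to 11), so Session 2 is a separate attendance. On allocation: "Participants will be randomly assigned to two different groups after they have finished assessment".

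SAP section 4 defines baseline as "Pre-treatment assessment". SAP section 6A specifies a mixed-effects repeated-measures ANOVA with group between subjects and "time (baseline, immediate post-treatment, 4-week, 12-week, 24-week) as a within-subjects factor".

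**The concern.** A single pain mark combines a person's stable level with variation specific to that day. In a change score the day-specific part enters twice, once at baseline and once at follow-up. The same baseline mark is shared by the changes to immediate post-treatment and to weeks 4, 12 and 24, so its noise runs through all of them.

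The plan neither documents the size of this noise nor reduces it, although participants are back in the laboratory, still unstimulated, at Session 2. With 30 per group, precision is worth having when it costs one more mark at a visit already scheduled. What is at stake is the width of the interval for pain change, and the strength of the planned correlations of VAS change with LEP, EEG and rsfMRI measures.

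**Working it through.** **The plan's own figure.** SAP section 3 gives 60 participants (30 per group), 80% power, a 1.1 cm difference and a significance level of 0.05. No SD is stated, so 60 cannot be reproduced forwards. Solving backwards with a two-sided two-sample t-test, 30 evaluable per arm and 80% power require d = 0.736, that is SD = 1.1/0.736 = 1.50 cm. The SAP does not say whether this SD refers to a single mark or to a change. The steps below therefore use only d = 0.736 as the 80% reference point.

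**Inputs that the documents do not give (assumptions).** Let ρ be the share of single-mark variance that is stable between days, 0.6-0.9. Let s be the correlation of the stable part between baseline and follow-up, 0.8-0.9. Single-mark variance is scaled to 1. The correlation between two pre-stimulation marks is then ρ, and the pre-post correlation is r = ρs.

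**Variance of one post-minus-baseline change**, with k baseline marks averaged and one follow-up mark:

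Var = 2ρ(1 − s) + (1 − ρ)/k + (1 − ρ)

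The proportional cut from k = 1 to k = 2 is (1 − ρ)/[4(1 − r)]. It does not depend on the SD.

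| ρ | s | r | Var, 1 mark | Var, 2 marks | Cut | Power, from 80% |
|---|---|---|---|---|---|---|
| 0.6 | 0.8 | 0.48 | 1.04 | 0.84 | 19.2% | 87.6% |
| 0.6 | 0.9 | 0.54 | 0.92 | 0.72 | 21.7% | 88.6% |
| 0.9 | 0.8 | 0.72 | 0.56 | 0.51 | 8.9% | 83.5% |
| 0.9 | 0.9 | 0.81 | 0.38 | 0.33 | 13.2% | 85.2% |

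Power is for 30 per arm with effect 0.736/√(1 − cut). A simulation of 400,000 draws agrees with the formula: pre-post correlation 0.6 with between-mark correlation 0.85 gave 9.2% (formula 9.4%), and with 0.65 gave 21.6% (formula 21.9%).

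**Wider assumptions.** Take pre-post correlations of 0.3-0.8 and between-mark correlations of 0.5-0.95, the latter never below the former. The cut is 0.05/(4 × 0.7) = 1.8% at the least favourable corner. It is exactly 25% wherever the two correlations are equal. The range is therefore about 2-25%.

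**If baseline is a covariate.** Residual variance is 1 − r² with one mark and 1 − 2r²/(1 + ρ) with the mean of two.
- ρ = 0.9, s = 0.8: 0.4816 falls to 0.4543, a cut of 5.7%.
- ρ = 0.75, s = 0.9 (r = 0.675): 0.5444 falls to 0.4793, a cut of 12.0%.

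Over the whole grid the extra mark gives about 6-12%. Adjusting for the existing single mark already cuts variance by (1 − r)/2 relative to a change score: 9.5% at r = 0.81 and 26% at r = 0.48.

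**Which contrasts are affected.** The five-level group-by-time interaction has four degrees of freedom. Three can be written as contrasts among the four post-treatment times and contain no baseline term. The figures above apply to a single post-minus-baseline contrast, which the SAP does not single out as primary.

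**The case against.** A reader might infer from the VAS paragraph that the plan treats the baseline as free of error. The documents do not support that. The sentence compares the scale with other pain tools, and in the SAP's model baseline is a response with its own residual error.

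A reader might also infer that the noise widens every comparison between arms. It does not. A post-hoc comparison of active with sham at one post-treatment time contains no baseline term.

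The stronger objections are these.

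- **No error in the plan is shown.** Randomisation protects the comparison from bias. Because the SAP gives no SD, the planned 80% may already allow for single-mark noise. This stands: the point is an efficiency gain, and it does not show that the trial is underpowered.
- **The size is uncertain.** The VAS sheet is not in the supplied text. If it asks about, say, the past week, part of the daily variation is already averaged out and two marks close together would overlap. The gap between Sessions 1 and 2 is not stated. The protocol also mentions a VAS during a Phase I that the supplied text does not define, although the session lists show none between Sessions 1 and 11. This stands, and is why the result is given as a range.
- **Covariate adjustment is cheaper.** It needs no new data and brings a gain of similar order. This stands, but the second mark still adds about 6-12% on top.
- **The second mark may follow allocation** and falls on the first treatment day, when anticipation could shift ratings. Under an intact blind any shift should be alike in both arms, and it can be avoided by timing the allocation differently.
- **The study was discontinued** and reports descriptive statistics only. The SAP's deviation note also says that ways to resume are being explored, so the point is of use only in that event.

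**Conclusion.** The point holds as a low-cost improvement in precision. There is one pre-treatment VAS mark, participants return before any stimulation, and the planned analysis carries the noise in that mark into each change from baseline. Under the stated assumptions, averaging in a second mark lowers the variance of a single post-minus-baseline change by 9-22%, equivalent to raising 80% power to about 84-89%. The range is about 2-25% under wider assumptions, and about 6-12% once baseline is a covariate. All of these rest on a reliability and a pre-post correlation that the documents do not give for the VAS. The direction of the effect is secure; its size is not.

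**What to change.** If the study resumes:

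1. At Session 2, administer the same VAS before electrodes are placed, under the blind, and preferably before the allocation is assigned or released.
2. Define baseline in SAP section 4 as the mean of the Session 1 and Session 2 marks.
3. In SAP section 6A, enter that mean as a covariate, or fit a mixed model with unstructured covariance. An averaged baseline has a smaller variance than the single follow-up marks, and the model must allow for this.
4. Keep the Session 1 mark alone as a sensitivity analysis. State how participants already enrolled, who have only that mark, will be handled.
5. Report the correlation between the two marks, so that a later sample-size calculation can use it.

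The cost is a protocol and SAP amendment and about one minute at Session 2. Unless randomisation is moved, the second mark falls after allocation, and the SAP should say so.

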What are the qualifications and training of the staff who will determine inclusion and exclusion?

Staff will be trained and supervised by [name] before the start of the study. In addition, all personnel involved at the study will have undergone research and ethical training at UTD and have taken and passed DOD required human subject training through CITI.

[name] is Associate Professor in the School of Behavioral and Brain Sciences at UT Dallas. [name] research focuses on understanding the neural mechanisms underlying disorders (e.g. tinnitus, fibromyalgia, pain) and to develop novel invasive and non-invasive neuromodulation treatments for those who suffer from these disorders. He has also run a large scale clinical trials in human subjects using Vagus Nerve Stimulation.

[name] is a Johns Hopkins trained neurologist is also a Professor of Behavioral and Brain Sciences with a joint appointment in the departments of Neurology and Psychiatry at The University of Texas Southwestern Medical Center at Dallas. [name] work has focused on how the brain stores and retrieves memory and applying these findings to investigate dysfunction in this area in patient populations. He has also run large scale investigations in Herpes Simplex Encephalitis, West Nile Virus encephalitis, Gulf War Illness, and PTSD.

[name] is has been designing and conducting (HD) tDCS studies in different research populations for [name] and [name] laboratory in the past 3 years. She has a doctoral degree is in Clinical Psychology and has several years

Last Revised 01/2016 Page 8 of 22

experience in human subjects research.

[name] is a speech pathologist who is now obtaining her Ph.D. in cognitive neuroscience in [name] laboratory. She is trained to administer EEG and apply different neuromodulation techniques (tDCS, TMS, VNS) and has been working in the lab for almost 2 years. She will be supervised by both [name].

Research staff will be trained to monitor all screening and assessment materials for indications of clinically significant symptomatology (e.g., depression, suicidal ideations) and tDCS safety and adverse effects. Data on possible adverse effects will be monitored and discussed in weekly lab meetings by all staff, including study doctor ([name] clinically significant symptomatology be identified, [name] will determine whether consultation with the participant is warranted and whether referral for further evaluation and treatment is necessary.

election procedures

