- 1. VAS. The Visual Analogue Scale
- 2. MFIS. Modified Fatigue Impact Scale
- 3. PSQI. Pittsburgh Sleep Quality Index
- 4. BDI. Beck Depression Inventory
- 5. PCS. Pain Catastrophizing Scale
- 6. MGPQ. McGill Pain Questionnaire
- 7. PVAQ. Pain Vigilance and Awareness Questionnaire
- 8. Resting state EEG.

Last Revised 01/2016 Page 15 of 22

Confirm that you will not have access to, or create a link, which would make it possible to identify participants.

sociological or legal consequences for the participant from which it originated?

If yes, describe the potential negative consequences.

If this record or specimen became publicly available, could it have negative psychological, physical, economic,

Confirm that the data/specimens you wish to review already exist.

The data set does not already exist

Yes No

I will not have access to, or create a link.

I will have access to a link, explain:

The data set exists

Last Revised 01/2016 Page 16 of 22

RISK/BENEFIT ASSESSMENT

A reasonable person would consider it to be important to know the risk of harm or discomfort when deciding whether to participate in the research project.

-			D . 1	
የሰ	ten	าราลา	Risk	2

Are there risks of physic	al harm or discomfort associated with the research?
⊠ Yes □ No	
	The most common side effect of neurostimulation is temporally local redness of the skin direct under the electrode. This disappears within $1\ \text{hour.}$
	 Itching at the site of the electrode, passing within the hour Slight feeling of dizziness when starting the stimulation occurs in a small number of patients. This takes only a few seconds and does not affect balance after stimulation Very rarely, temporary skin damage may occur under the electrode. This gives a darkening of the skin, which normalizes after a week and heals. The size of such etch is a few millimeters. This is harmless with the current that we will handle, this risk is minimal.
	On the safety of transcranial direct current stimulation in healthy volunteers, in 2005 a well-conducted study published in the Journal of Neurology. There is a group of 103 people total transcranial direct current stimulation given to 2 mA. Outside redness and itching they describe a transient slight improvement in language fluency (pronouncing words) or a transient slight delay in language fluency. The technique is considered safe.
Are there risks of psycho	ological harm or discomfort associated with the research procedure?
☐ Yes ⊠ No	
If yes, describe:	

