### 3. Sample Size and Power

- **Primary Outcome:** Pain severity on the Visual Analogue Scale (VAS).
- **Secondary Outcomes:** Questionnaire measures (MFIS, PSQI, BDI, PCS, MGPQ, PVAQ) and neurophysiological measures (LEP, EEG, rsfMRI).
- **Sample Size:** 60 participants (30 per group), allowing an 80% power to detect a 1.1 cm difference on the VAS scale (Cohen's d effect size) with a significance level of 0.05. The design anticipates a 10% dropout rate.

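### The plan says adverse effects will be monitored but names no method of asking about or recording them, and the SAP has no harms summary by arm

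*Protocol*

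**What the plan says.** **Monitoring.** The protocol's section on staff qualifications says research staff will be trained to watch screening and assessment materials for significant symptoms and for tDCS safety and adverse effects. It adds: "Data on possible adverse effects will be monitored and discussed in weekly lab meetings by all staff". It names no instrument, no time of asking and no recording form.

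**Sessions.** The protocol's account of participant activities lists Sessions 2-10 as stimulation only, about 45 minutes each. At Session 11 the post-stimulation battery is introduced as "Immediate Post-tDCS Assessment - Participants will complete the following assessments that were part of the Pre-tDCS assessment". It consists of seven questionnaires (VAS, MFIS, PSQI, BDI, PCS, MGPQ, PVAQ) and resting EEG, and the four follow-up visits repeat it. None of these is presented as a side-effect question.

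**Expected effects.** Under Potential Risks the protocol lists:
- "temporally local redness of the skin direct under the electrode", gone within an hour;
- "Itching at the site of the electrode, passing within the hour";
- slight dizziness when stimulation starts, of which it says "This takes only a few seconds and does not affect balance after stimulation";
- very rarely, darkening of the skin that settles after about a week.

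**SAP.** Section 3 makes VAS pain the primary outcome and gives the secondary outcomes as "Questionnaire measures (MFIS, PSQI, BDI, PCS, MGPQ, PVAQ) and neurophysiological measures (LEP, EEG, rsfMRI". Sections 6 to 8 contain no safety outcome and no comparison or table of harms.

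**The concern.** A weekly meeting can review only what has already been written down. Two of the expected effects are felt rather than seen, and they end within seconds or an hour. If nobody asks at the session, they reach the record only when a participant mentions them. An event that was never recorded cannot be recovered by a later analysis, so this is a question of collection as well as of a missing table.

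At stake is what the randomised sham comparison can say about harm. The protocol describes Gulf War Illness as chronic with many symptoms, so some complaints will arise whatever stimulation is given. Asking the same question in both arms is what separates that background from an effect of stimulation. The one safety study the protocol describes was in healthy volunteers, so this trial is a natural place to obtain such data in the target population.

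**Working it through.** The documents give no adverse-effect rate and no share of events captured, so there is no planned safety figure to reproduce. The only planned figure used below is 30 participants per group (SAP section 3). The point does not depend on the power calculation.

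**1. Where could the effects be recorded?** Ten stimulation sessions are planned (SAP section 4), which are protocol Sessions 2-11.
- Sessions 2-10 (nine of the ten): no assessment listed.
- Session 11 and the four follow-ups: seven scales plus EEG, with no side-effect item listed.
- Consent discussion: participants are asked what they should do if they have symptoms. That is a route for volunteered reports.
- Minimizing Risks: professional staff monitor the experiments. That is observation.
- Data Privacy section: adverse events go to the funder's protection office. That is onward reporting.

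None of these states a systematic method of asking.

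**2. Which effects would passive collection miss?**

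| Effect | Stated duration | Visible to staff? |
|---|---|---|
| Redness | within 1 hour | yes, when the electrode is removed |
| Itching | within the hour | no |
| Dizziness | a few seconds | hardly |
| Skin darkening | about a week | yes, also at a later weekday session |

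The exposure is therefore mainly for itching and dizziness.

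**3. What would incomplete capture do?** These are illustrations on assumed rates. Let p be the true proportion of participants affected and c the share of them recorded. Then recorded rate = c × p, and recorded difference = c(active) × p(active) − c(sham) × p(sham).

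Same c in both arms, assumed p = 30% active and 10% sham, 30 per arm:
- c = 1: 9 versus 3 participants; difference 20 points.
- c = 0.5: 4.5 versus 1.5; difference 10 points.
- c = 0.25: 2.25 versus 0.75; difference 5 points.

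Different c by arm:
- True rates 30% in both arms, c = 0.75 active and 0.5 sham: 22.5% versus 15%, a false difference of 7.5 points.
- True rates 30% and 10%, c = 0.25 active and 0.75 sham: 7.5% versus 7.5%, so a real difference of 20 points disappears.

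Each arm's rate is too low whenever c is below 1, but the contrast can err in either direction.

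**4. What would zero recorded events mean?** With 0 of 30, the one-sided 95% upper bound is 1 − 0.05^(1/30) = 9.5%. This bounds c × p, so the bound on p is 9.5%/c: 9.5% at c = 1, 19.0% at c = 0.5, and 28.5% at c = 1/3. If c is unknown, there is no usable bound.

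**The case against.** The strongest reply is that silence is not absence. The monitoring sentence presupposes that adverse-effect data exist, and staff are said to be trained on tDCS safety. The session lists are also demonstrably incomplete: LEP, rsfMRI, the treatment guess and the check on medication changes are all in the SAP, and none appears in the protocol's lists. The stimulation visits last about 45 minutes for 20 minutes of current, with the rest not itemised. The form asks for instruments to be attached, and the attachments are not in the text. All of this stands. A reader might infer that side effects are never asked about, or are counted only if noticed or volunteered; the documents support only that the method is not stated.

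A reader might also infer that the harm rates in this trial are too low. That follows only if capture is incomplete, and the documents do not show how complete it was. Nor does the argument reach every effect: participants return each weekday, so week-long skin darkening would probably be seen, and redness is visible when the electrode comes off.

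Finally, repeated questions about sensations might draw attention to allocation in a double-blind sham trial. That is a genuine cost of the remedy, though a small one.

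What the reply does not remove is the gap itself. No place in either document says who asks, when, or how events are recorded by session and arm, and the SAP plans no harms summary of any kind.

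**Conclusion.** The point holds as a gap in specification, in two parts: no stated method of eliciting and recording adverse effects, and no safety outcome or by-arm harms summary in the SAP. If collection is passive, itching and dizziness are the effects most exposed to undercounting; redness and skin darkening are less so.

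The size of any undercount cannot be derived from the documents. The figures above rest on assumed event rates and capture shares and show only the mechanism. With equal capture in both arms, a difference shrinks in proportion; with unequal capture, it may be inflated, hidden or reversed.

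This is a cheap improvement rather than a flaw in the efficacy analysis. The trial was discontinued and currently reports descriptive statistics only (SAP, deviation statement). A new form would therefore help only if the trial resumes, and it cannot supply solicited data for the present report.

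**What to change.** **If the trial resumes.**
- State in the protocol who asks about adverse effects, when, and on what form.
- Add a short checklist of the effects named under Potential Risks, plus free text. Ask it in the same words in both arms at the end of each stimulation session (Sessions 2-11) and at each follow-up, and record answers by session and date.
- Add a SAP safety section giving the number and proportion of participants with each effect by stimulation received, with exact 95% confidence intervals, and the between-arm difference.

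**For data already collected.** Include any recorded adverse effects by arm in the descriptive report. Label them as not systematically solicited unless the records show otherwise, and do not present an absence of reports as evidence of a low rate.

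**Cost.** About a minute per session, one form and one table. Prompting will bring in some trivial reports. There is a small risk that asking about sensations draws attention to allocation; the treatment guess already planned in SAP section 8 can help to check this.
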